## 5.1.2 Hypotheses and Statistical Methods for Secondary Objectives

The Per-Protocol Analysis Set (PPAS) will be used as the primary analysis set for the secondary objectives.

### 5.1.2.1 Hypotheses

### 5.1.2.1.1 Geometric Mean Titers

For each of the 4 virus strains, the post-final vaccination GMTs in subjects 6 to < 36 months of age who receive the 0.5-mL dose of Fluzone Quadrivalent vaccine will be non-inferior to the post-final vaccination GMTs in those subjects who receive the 0.25-mL dose of Fluzone Quadrivalent vaccine.

### 5.1.2.1.2 Seroconversion

For each of the 4 virus strains (A/H1N1, A/H3N2, B1 and B2), the seroconversion rates in subjects 6 to < 36 months of age who receive the 0.5-mL dose of Fluzone Quadrivalent vaccine will be non-inferior to the seroconversion rates in those subjects who receive the 0.25-mL dose of Fluzone Quadrivalent vaccine.

## 5.1.2.2 Statistical Methods

### 5.1.2.2.1 Geometric Mean Titers

The statistical methodology will be based on a 2-sided 95% CI of the ratio of the GMTs (0.5-mL dose divided by 0.25-mL dose) at 28 (window, 28–35) days after the final vaccination.

Non-inferiority for GMTs will be demonstrated if the lower limit of the 2-sided 95% CI of the GMT ratio is > 0.667 for each of the 4 virus strains (A/H1N1, A/H3N2, B1 and B2). The 95% CI will be calculated using normal approximation of log-transformed titers.

For the separately virus strain (A/H1N1, A/H3N2, B1 and B2), the primary parameter will be the difference of the means of the log10-transformed post-vaccination titers between GMT0.5mL and GMT0.25mL.

Each hypothesis will be supported by the data if the upper bound of the calculated 95% CI is > 0.667. This is the equivalent to testing the null hypothesis using a 1-sided type I error rate of 0.025.

For each virus strain (A/H1N1, A/H3N2, B1 and B2), the null hypothesis and the alternative hypothesis, are:

$$H_0: \text{GMT}_{0.5\text{mL}} / \text{GMT}_{0.25\text{mL}} \leq 0.667$$

$$H_A: \text{GMT}_{0.5\text{mL}} / \text{GMT}_{0.25\text{mL}} > 0.667$$

or equivalently,

$$H_0: \log_{10}(\text{GMT}_{0.5\text{mL}}) - \log_{10}(\text{GMT}_{0.25\text{mL}}) \leq \log_{10}(0.667)$$

$$H_A: \log_{10}(\text{GMT}_{0.5\text{mL}}) - \log_{10}(\text{GMT}_{0.25\text{mL}}) > \log_{10}(0.667)$$

For the separately considered GMT hypotheses, if the null hypothesis is rejected, then the alternative hypothesis of non-inferiority will be supported.

The 2-sided 95% CI for the ratio of GMTs (GMT0.5mL / GMT0.25mL) will be calculated using normal approximation of log-transformed concentrations.

The 95% CI for the GMT ratio between 2 groups will be constructed as follows: Logarithm transformation of the individual concentrations will be calculated. Assuming that individual log10 (concentration) is normally distributed, the 95% CI for the difference in log10 (GMT) between 0.5-mL (or Groupi) and 0.25-mL (or Groupj) will be in the form:

$$\bar{X}_i - \bar{X}_j \pm t(1-\alpha/2, n_i + n_j - 2) \times S \sqrt{1/n_i + 1/n_j}$$

where  $\bar{X}_i = \log_{10}$  (GMC) is the mean of log10 (concentration) of Group *i*,

$S^2 = [(n_i - 1) S_i^2 + (n_j - 1) S_j^2] / (n_i + n_j - 2)$  is the pooled sample variance,

$n_i$  and  $S_i^2$  are the sample size and sample variance of Group *i*,

$t(1-\alpha/2, n_i + n_j - 2)$  is the 100(1- $\alpha$ /2) percentile of the *t*-distribution with degrees of freedom  $df = n_i + n_j - 2$ .

For descriptive purposes, the statistics presented in Table 5.1 will be produced.

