Schedule of Study Procedures:	
Vaccination
 
All subjects will receive 1 intramuscular injection of Fluzone Quadrivalent vaccine (0.25 mL [Group 1] or 0.5 mL [Group 2]) at Visit 1. For subjects for whom 2 doses of influenza vaccine are recommended per ACIP guidance, a second intramuscular injection of influenza vaccine (same 0.25-mL or 0.5-mL dose as administered at Visit 1) will be administered at Visit 2.
 
Blood Sampling
 
A total of 2 blood samples of approximately 5 mL each will be collected from a planned subset of 1600 subjects randomly selected by an IRT system (half in Group 1 and half in Group 2).
 
The first blood sample will be collected at Visit 1 prior to vaccination. The second blood sample will be collected at Visit 2, if no study vaccine is administered at Visit 2; or at Visit 3, if study vaccine is administered at Visit 2.
 
Study sites, at their discretion, may apply a topical analgesic to the venipuncture site prior to obtaining sera. However, topical analgesic agents must not be applied at the site of vaccine administration.
 
Collection of Safety Data
 
Staff will observe subjects for 20 minutes following vaccine administration and will record the occurrence of any immediate unsolicited systemic AEs. Parents/guardians will record information about solicited injection site and

	
systemic reactions from Day 0 to Day 7 after each vaccination, and will record information about unsolicited non-serious AEs and SAEs from Visit 1 to Visit 2 for subjects receiving 1 dose of study vaccine and from Visit 1 to Visit 3 for subjects receiving 2 doses of study vaccine.
 
 • Staff will contact parents/guardians by telephone at Day 8 (window, Days 8–10) after any study vaccine administration to remind parents/guardians to record any AEs experienced and any concomitant medications taken from the most recent visit to the next visit in the diary card and to bring the diary card with them to the next visit. Parents/guardians will also be reminded to notify the site immediately if an SAE occurs. • Staff will review the safety data with parents/guardians at Visit 2 for subjects receiving 1 dose of study vaccine, or at Visit 2 and Visit 3 for subjects receiving 2 doses of study vaccine.

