
Statistical Methods:
	
Summaries of the recruitment and baseline demographic characteristics of the study subjects will be presented. The number of subjects enrolled and their age at enrollment (mean, median, and minimum and maximum), sex, race, and ethnic origin will be summarized, along with the number and description of protocol violations.
 
Continuous variables will be summarized by descriptive statistics (e.g., means and standard deviations for the non-immunogenicity endpoints, and geometric means and their confidence intervals [CIs] for the immunogenicity endpoints); categorical variables will be summarized by frequency distributions (frequency counts, percentages, and their CIs for the main endpoints).
 
Primary Objective: Safety
 
The 0.5-mL dose of Fluzone Quadrivalent vaccine will be demonstrated as non-inferior to the 0.25-mL dose of Fluzone Quadrivalent vaccine in terms of fever reaction through an assessment of the rates of any fever (temperature $\geq 100.4^{\circ}\text{F}$ [38.0°C]) during the 7 days following any dose (Dose 1 and Dose 2 combined). Non-inferiority will be demonstrated if the upper bound of the 2-sided 95% CI of the rate difference between Group 2 (subjects receiving 0.5 mL of vaccine) and Group 1 (subjects receiving 0.25 mL of vaccine) is $< 5\%$. The 95% CI of the rate difference will be computed using the Wilson Score method without continuity correction. The Safety Analysis Set will be used for this objective.
 
Secondary Objective: Immunogenicity
 
Geometric mean titers: The statistical methodology will be based on a 2-sided 95% CI of the ratio of the GMTs (0.5-mL dose divided by 0.25-mL dose) at 28 (window, 28–35) days after the final vaccination. Non-inferiority for GMTs will be demonstrated if the lower limit of the 2-sided 95% CI of the GMT ratio is > 0.667 for each of the 4 virus strains. The 95% CI will be calculated using normal approximation of log-transformed titers. The Per-Protocol Analysis Set (PPAS) will be used as the primary analysis set for this objective.
 
Seroconversion: The statistical methodology will be based on a 2-sided 95% CI of the difference in seroconversion rates (0.5-mL dose minus 0.25-mL dose) at 28 (window, 28–35) days after the final vaccination. Non-inferiority for seroconversion will be demonstrated if the lower limit of the 2-sided 95% CI is $> -10\%$ for the 4 strains. The 95% CI of the rate difference will be computed using the Wilson Score method without continuity correction. The PPAS will be used as the primary analysis set for this objective.

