2.3.3 Serum Collection

[REDACTED]

There are no endpoints for the serum collection objective.

3 Investigators and Trial Organization

This trial will be conducted in approximately 38 centers in the United States. Details of the trial centers, the Investigators at each center, and the Coordinating Investigator(s) are provided in the “List of Investigators and Centers Involved in the Trial” document.

The Sponsor’s Responsible Medical Officers (RMOs) (the persons authorized to sign this protocol and any amendments on behalf of the Sponsor) are [REDACTED] or such delegate(s) as may be identified in their absence.

4 Institutional Review Board

Before the investigational product can be shipped to the investigational site and before the inclusion of the first subject, this protocol, the informed consent form(s) (ICF[s]), subject recruitment procedures, and any other written information to be provided to subjects must be approved by, and/or receive favorable opinion from, the appropriate Institutional Review Board(s) (IRB[s]).

In accordance with Good Clinical Practice (GCP) and local regulations, each Investigator and/or the Sponsor are responsible for obtaining this approval and/or favorable opinion before the start of the trial. If the protocol is subsequently amended, approval must be re-obtained for each substantial amendment. Copies of these approvals, along with information on the type, version number, and date of document, and the date of approval, must be forwarded by the Investigator to

the Sponsor together with the composition of the IRB(s) (the names and qualifications of the members attending and voting at the meetings).

The Investigator will submit written summaries of the status of the trial to the IRB(s) annually, or more frequently if requested. All serious adverse events (SAEs) occurring during the trial that are related to vaccination will be reported by the Investigator to the IRB(s), according to IRB policy.

5 Investigational Plan

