5.1.3 Trial Plan

Using a pre-programmed interactive response technology (IRT) system, subjects will be randomly assigned in a 1:1 ratio to either 1 of the following groups:

- Group 1: 0.25 mL of Fluzone Quadrivalent vaccine (approximately 1095 subjects)
- Group 2: 0.5 mL of Fluzone Quadrivalent vaccine (approximately 1095 subjects)

Enrollment will be stratified by age at each site so that approximately 50% of subjects at each site will be 6 to < 24 months of age and approximately 50% of subjects at each site will be 24 months to < 36 months of age. If necessary to achieve 50% overall enrollment of subjects 6 to < 24 months of age, individual sites may be permitted to deviate from this ratio.

All subjects will receive 1 intramuscular dose of Fluzone Quadrivalent vaccine (0.25 mL [Group 1] or 0.5 mL [Group 2]) during Visit 1. For subjects for whom 2 doses of influenza vaccine are recommended per ACIP guidance, a second dose of Fluzone Quadrivalent vaccine (same 0.25-mL or 0.5-mL dose as administered at Visit 1) will be administered during Visit 2 (28 [window, 28–35] days after Visit 1).

Blood specimens will be obtained from a planned subset of 1600 subjects randomly selected by an IRT system (half in Group 1 and half in Group 2) prior to the first vaccination and 28 (window, 28–35) days following the final vaccination (Visit 2 for subjects receiving 1 dose; Visit 3 for subjects receiving 2 doses) and assayed for immunogenicity.

Solicited AE information will be collected for 7 days after each vaccination. Unsolicited AE information and SAE information will be collected from Visit 1 to Visit 2 for subjects receiving 1 dose or from Visit 1 to Visit 3 for subjects receiving 2 doses.

Note: Any SAE that occurs after a subject has completed the study but that is likely to be related to the product is to also be reported to the Sponsor.

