6.5 Randomization and Allocation Procedures

The Sponsor or designee will supply a centralized, computer-generated randomization code. Randomization of subjects will be performed with the permuted block method with stratification by site, age group, and vaccination schedule. Each subject who meets the inclusion/exclusion criteria will be randomly assigned according to his/her age group and vaccination schedule, to 1 of the 2 groups via an IRT system, according to a 1:1 ratio.

Before vaccination, authorized qualified study staff will contact the IRT system, enter identification and security information, and confirm a minimal amount of data in response to IRT system prompts. The IRT system will then state the vaccine dose identification number and whether the subject will be included in the immunogenicity subset. Subject numbers and vaccine dose identification numbers will be recorded on the eCRFs. The full procedures for randomization are detailed in the Operating Guidelines.

If the dose initially allocated for vaccination cannot be used (e.g., because the syringe broke or particulate matter was observed), authorized qualified study staff will obtain a replacement dose (see [Section 6.3.3](#)).

^a according to local regulations

Subject numbers should not be reassigned for any reason.

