12.1.2.2 Statistical Methods

- Geometric mean titers: The statistical methodology will be based on a 2-sided 95% CI of the ratio of the GMTs (0.5-mL dose divided by 0.25-mL dose) at 28 (window, 28–35) days after the final vaccination. Non-inferiority for GMTs will be demonstrated if the lower limit of the 2-sided 95% CI of the GMT ratio is > 0.667 for each of the 4 virus strains. The 95% CI will be calculated using normal approximation of log-transformed titers. The Per-Protocol Analysis Set (PPAS) will be used as the primary analysis set for this objective.
- Seroconversion: The statistical methodology will be based on a 2-sided 95% CI of the difference in seroconversion rates (0.5-mL dose minus 0.25-mL dose) at 28 (window, 28–35) days after the final vaccination. Non-inferiority for seroconversion will be demonstrated if the lower limit of the 2-sided 95% CI is $> -10\%$ for the 4 strains. The 95% CI of the rate difference will be computed using the Wilson Score method without continuity correction. The PPAS will be used as the primary analysis set for this objective.

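### The GMT-ratio interval leaves out baseline titer and the randomization strata: it is valid under the lower-limit rule, but wider than it need be if those factors predict titer

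*SAP*

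**What the plan says.** Protocol 6.5 states: "Randomization of subjects will be performed with the permuted block method with stratification by site, age group, and vaccination schedule". Section 3 adds: "This trial will be conducted in approximately 38 centers in the United States". Immunogenicity is assessed in "a planned subset of 1600 subjects randomly selected by an IRT system (half in Group 1 and half in Group 2", and the protocol does not say whether that subset is drawn within strata. On baseline sampling, the synopsis says "The first blood sample will be collected at Visit 1 prior to vaccination"; SAP 4.3.2.1 has these titers determined for each strain, in duplicate.

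The non-inferiority criterion in the protocol is that the "lower limit of the 2-sided 95% CI of the GMT ratio is > 0.667 for each of the 4 virus strains". On method, SAP 5.1.2.2.1 says "The 95% CI will be calculated using normal approximation of log-transformed titers" and gives the formula: the difference in mean log10 titer, plus or minus a t quantile on n_i + n_j - 2 degrees of freedom times the pooled SD times the root of 1/n_i + 1/n_j. There is no stratum or baseline term. Protocol 12.1.2.2 and the synopsis give the normal approximation without a formula and name no covariate. No visible text plans an adjusted GMT ratio, even as a sensitivity analysis.

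The same SAP section also contains this sentence: "Each hypothesis will be supported by the data if the upper bound of the calculated 95% CI is > 0.667". It contradicts the lower-limit rule stated a few lines above it.

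**The concern.** Stratified blocks make the two arms alike on site, age group and schedule, so spread between strata largely drops out of the dose contrast. The pooled variance still counts that spread, and it counts whatever spread baseline titer could explain. If these factors predict titer, the stated standard error is larger than the real one and the interval covers more than 95%.

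Under the lower-limit rule this cannot raise the risk of a false non-inferiority claim. The cost is precision of the reported ratio, and power when the true ratio is below 1. The power cost is larger for the decision than for one strain, because all four strains must pass. Prediction is plausible: schedule follows influenza vaccination history, and the protocol's rationale reports that dose differences in antibody response were greatest in the youngest children. Neither fact gives a size.

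**Working it through.** **Inputs from the documents.** Margin 0.667 on the ratio, log10(0.667) = -0.1759; 1-sided error 0.025; N = 2190; subset 1600 (800 per arm); about 38 sites.

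**Assumed, because Protocol 12.5 and SAP 5.5 are redacted.** SD of log10 titer 0.6 or 0.8; 12% random loss from the PPAS, giving 0.88 × 800 = 704 per arm; share of variance explained by the strata (Rs) and by strata plus baseline (Rt).

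**The plan's own figure.** At a true ratio of 0.667 the lower-limit rule has 1-sided error 1 - Φ(1.96) = 0.025, as the SAP states. Read literally, the upper-bound sentence would give Φ(1.96) = 0.975. What follows uses the lower-limit rule.

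**Width.** Adjusted/planned width is about √(1 - Rt).

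| Rt | √(1 - Rt) | Narrower by |
|---|---|---|
| 0.10 | 0.949 | 5% |
| 0.25 | 0.866 | 13% |
| 0.40 | 0.775 | 23% |

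In simulation with no predictive covariate, the adjusted interval was 0.3% wider.

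**Error of the planned interval.** Let q be the fraction of between-stratum variance that stratification removes from the contrast. Error = Φ(-1.96/√(1 - q·Rs)). If the subset keeps the strata balance, q = 0.88; if it is drawn without regard to strata, q = 0.88 × 1600/2190 = 0.643.

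| Rs | q = 0.88 | q = 0.643 |
|---|---|---|
| 0.10 | 0.0201 | 0.0214 |
| 0.20 | 0.0154 | 0.0179 |
| 0.30 | 0.0112 | 0.0146 |

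**Power at 704 per arm, Rs = 0.10, Rt = 0.25, q = 0.88.** With d = log10(ratio/0.667) and SE = SD·√(2/704):

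- planned: Φ((d - 1.96·SE)/(SE·√(1 - 0.88·Rs)))
- ANCOVA: Φ(d/(SE·√(1 - Rt)) - 1.96)

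Example, ratio 0.9 and SD 0.8: d = 0.1301 and SE = 0.0426. Planned power is Φ(1.143) = 87%; ANCOVA power is Φ(1.564) = 94%. The last column is the 4th power of the per-strain figure.

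| Ratio | SD | Per strain, planned → ANCOVA | All four, if independent |
|---|---|---|---|
| 1 | 0.6 | about 100% either way | about 100% either way |
| 1 | 0.8 | 98.8% → 99.7% | 95.4% → 99.0% |
| 0.9 | 0.6 | 98.6% → 99.7% | 94.7% → 98.8% |
| 0.9 | 0.8 | 87% → 94% | 58% → 78% |

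If the strains were fully correlated, the per-strain column would apply to the joint decision.

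**Site as a fixed effect.** With total explained variance of 25%, of which site contributes 0, 5 or 10 points, ANCOVA without site narrows the interval by 13.3%, 10.5% or 7.8%. With site it narrows it by 12.7% to 13.1% in all three cases. About 38 site terms therefore cost at most 0.4 points if site explains nothing.

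**Does ANCOVA hold its error?** Simulation at a true ratio of 0.667 used 20,000 trials per scenario (Monte Carlo SE 0.0011), with 38 uneven sites, assumed blocks of 4, 12% loss, and two-dose shares of 65% (younger) and 35% (older). The subset was balanced on strata.

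| Variance from site / age + schedule / baseline | Planned t | ANCOVA with site |
|---|---|---|
| 0 / 10% / 15% | 0.0209 | 0.0262 |
| 5% / 10% / 10% | 0.0174 | 0.0254 |
| 10% / 10% / 5% | 0.0133 | 0.0215 |

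Across 13 scenarios ANCOVA with site averaged 0.0252. The 0.0215 lies about three Monte Carlo SEs below 0.025, on the conservative side.

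**Floored baselines.** Titers below 10 are entered as 5. With 35%, 62% or 85% of children at that floor, baseline still added 12, 9.5 or 6 points of R² under one assumed titer model. ANCOVA intervals were then 17.5%, 16.1% or 13.9% narrower, with error 0.0249, 0.0237 and 0.0270 (10,000 trials each, Monte Carlo SE 0.0016).

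**The case against.** The strongest reply is that nothing is broken. A fully prespecified unadjusted GMT ratio is a legitimate choice, its error is conservative, GMT is a secondary endpoint, and baseline already enters through seroconversion and fold-rise. The documents expect generally higher titers with the full dose. At a ratio of 1.1 and SD 0.8, the formulas above give joint power for four independent strains of 99.8% planned and 99.98% adjusted.

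The largest gain, 58% to 78%, needs all four strains at 0.9, SD 0.8 and independence, although the titers come from the same children. At an assumed between-strain correlation of 0.5 it becomes 69% to 83%; at 0.7, 74% to 86%. SD, R² and loss are all assumed. Replacing a confirmatory method late in the trial also invites challenge.

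Most of this stands, and it limits the point to efficiency. It does not remove it. Adjustment keeps the estimand and margin, uses data already collected, and costs about 0.3% in width if the covariates turn out useless. The timing argument bears on whether ANCOVA should be confirmatory or supportive, not on whether to prespecify it. The upper-bound sentence is a separate defect and lends no weight to the efficiency argument.

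**Conclusion.** The concern holds. The SAP formula uses neither the randomization strata nor baseline titer. If they predict titer, the interval is conservative and wider than necessary: about 13% at an assumed 25% of variance explained, and no gain at zero. Validity is affirmed only for the lower-limit rule.

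The effect on the decision is small at a true ratio of 1 or above. It becomes material only if the ratio is below 1 and titers are variable. The change is worth making but not essential. Confidence in the size is moderate, because no SD, R², two-dose share or loss rate can be seen in the documents.

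**What to change.** Before unblinding, prespecify an ANCOVA of log10 post-final-vaccination titer on dose group, log10 baseline titer, age group, vaccination schedule and site (fixed effect, small sites pooled by a rule set in advance). Keep the 0.667 margin on the lower limit, and keep the planned interval as supportive. The ANCOVA estimates the same difference in log10 means, so the ratio keeps its meaning.

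For a missing baseline, enter a constant plus a missing-baseline indicator so that no child is lost. In one simulated setting with 5% of baselines missing, the interval was 21.6% narrower, against 22.2% with none missing, and the error was 0.0250. SAP 5.3.2 bars imputation, so amend it to allow this for the covariate only, and check the redacted Protocol 12.3.2. The visible PPAS exclusions require a valid post-vaccination result only, but the lead-in text is not visible.

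Correct the upper-bound sentence in SAP 5.1.2.2.1 to the lower limit. Align Protocol 12.1.2.2 and the synopsis, and record the change in SAP 5.7, which now reads as not applicable.

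As the confirmatory method, this would mean a protocol amendment; under Protocol 5.4, one judged substantial needs IRB approval and must be forwarded to the regulators. Time is short, with the last visit planned for February 2017. If it is too late, leave the confirmatory method alone and add the ANCOVA as a prespecified sensitivity analysis in the CSR appendices, as the SAP does for the analysis without Site 009. That costs SAP text and a few lines of code. No new data are needed, and no change is asked for fever or seroconversion.

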### 5.1.1.2 Statistical Methods

The 0.5-mL dose of Fluzone Quadrivalent vaccine will be demonstrated as non-inferior to the 0.25-mL dose of Fluzone Quadrivalent vaccine in terms of fever reaction through an assessment of the rates of any fever (temperature  $\geq 100.4^{\circ}\text{F}$  [ $38.0^{\circ}\text{C}$ ]) during the day of vaccination or during the 7 days following any dose (Dose 1 and Dose 2 combined).

Non-inferiority will be demonstrated if the upper bound of the 2-sided 95% CI of the rate difference between Group 2 (subjects receiving 0.5 mL of vaccine) and Group 1 (subjects receiving 0.25 mL of vaccine) is  $< 5\%$ . The 95% CI of the difference in proportions  $P_{0.5\text{mL}} - P_{0.25\text{mL}}$  will be computed using the Wilson Score method without continuity correction as quoted by Newcombe (3).

To test this hypothesis, a 2-sided 95% CI will be constructed around the difference,  $P_{0.5\text{mL}} - P_{0.25\text{mL}}$ , where  $P_{0.25\text{mL}}$  and  $P_{0.5\text{mL}}$  are the proportions of subjects in Group 1 and Group 2, respectively, experiencing any fever (temperature  $\geq 100.4^{\circ}\text{F}$  [ $38.0^{\circ}\text{C}$ ]) during the day of vaccination or during the 7 days following any dose (Dose 1 and Dose 2 combined).

The hypothesis will be supported by the data, if the upper bound of the calculated 95% CI is  $< 5\%$ . This is the equivalent to testing the null hypothesis using a 1-sided type I error rate of 0.025.

$$H_0: P_{0.5\text{mL}} - P_{0.25\text{mL}} \geq 5\%$$

$$H_A: P_{0.5\text{mL}} - P_{0.25\text{mL}} < 5\%$$

If the null hypothesis is rejected, then the alternative hypothesis of non-inferiority will be supported.

Because of concerns regarding the integrity of safety data collected at Site 009, an additional statistical analysis will be conducted that excludes temperature data collected at this site. The results of this analysis will be reported in the CSR appendices.

Nevertheless, the study conclusion (non-inferiority with respect to the proportion of subjects with fever in Group 1 vs Group 2) will be based on the primary analysis that includes data from Site 009.

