#### 5.1.2.2.2 Seroconversion

The statistical methodology will be based on a 2-sided 95% CI of the difference in seroconversion rates (0.5-mL dose minus 0.25-mL dose) at 28 (window, 28–35) days after the final vaccination. Non-inferiority for seroconversion will be demonstrated if the lower limit of the 2-sided 95% CI is  $> -10\%$  for the 4 strains (A/H1N1, A/H3N2, B1 and B2). The 95% CI of the rate difference will be computed using the Wilson Score method without continuity correction.

For each virus strain (A/H1N1, A/H3N2, B1 and B2), the null hypothesis and the alternative hypothesis, are:

$$H_0: P_{0.5mL} - P_{0.25mL} \leq -10\%$$

$$H_A: P_{0.5mL} - P_{0.25mL} > -10\%$$

For the separately considered seroconversion hypotheses, if the null hypothesis is rejected, then the alternative hypothesis of non-inferiority will be supported.

The CI of the difference in proportions  $P_{0.5mL} - P_{0.25mL}$  will be computed using the Wilson Score method without continuity correction, quoted by Newcombe (3).

For descriptive purposes, the statistics presented in Table 5.1 will be produced.

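### SAP 5.1.2.2.1 gives two conflicting decision rules for GMT non-inferiority: lower limit above 0.667, then upper bound above 0.667

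*SAP*

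**What the plan says.** SAP 5.1.2.2.1 (Geometric Mean Titers) bases the test on a "2-sided 95% CI of the ratio of the GMTs (0.5-mL dose divided by 0.25-mL dose"), so a larger ratio favours the 0.5-mL dose. It then gives the criterion twice.

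- First statement: "Non-inferiority for GMTs will be demonstrated if the lower limit of the 2-sided 95% CI of the GMT ratio is > 0.667", to be met for each of the four strains.
- Second statement, shortly after: "Each hypothesis will be supported by the data if the upper bound of the calculated 95% CI is > 0.667". The next sentence adds: "This is the equivalent to testing the null hypothesis using a 1-sided type I error rate of 0.025".

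The same section sets the null hypothesis as a ratio at or below 0.667 and the alternative as a ratio above 0.667, on both the ratio and the log10 scale.

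The protocol (Synopsis, Statistical Methods; and section 12.1.2.2) gives only the lower-limit rule. SAP 5.7 records no change to the planned analyses, so no deliberate switch is declared.

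**The concern.** The two statements are different decision rules for one test. To reject a null hypothesis that the ratio is at or below 0.667, the whole interval must lie above 0.667, which means its lower limit must. An upper bound above 0.667 shows only that inferiority beyond the margin has not been proven. A wide interval from poor data would pass that criterion easily.

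GMT non-inferiority is one of the two parts of the secondary immunogenicity objective, which has formal hypotheses and margins. The analysis is programmed from the SAP, and one of its two sentences does not control type I error although it is described as doing so. If a strain's interval contained 0.667, someone would have to choose between the two sentences after seeing the result.

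**Working it through.** **Inputs.** From SAP 5.1.2.2.1: margin 0.667; two-sided 95% interval; difference of log10 means with pooled variance S² and a t quantile on n₁ + n₂ − 2 degrees of freedom; stated one-sided error 0.025. From SAP 3.2: an immunogenicity subset of about 1600, half in each group, so about 800 per group before exclusions. The SD and the sample-size text are blacked out (protocol 12.5, SAP 5.5). The SD and the evaluable number are therefore assumptions below, and the main result does not need them.

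**Step 1: the plan's own figure.** Let T = (observed log10 ratio − log10 0.667) / (S√(1/n₁ + 1/n₂)) and let t* be the 97.5% t quantile.

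- Lower limit > 0.667 is the event T > t*.
- Upper bound > 0.667 is the event T > −t*.

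At a true ratio of 0.667, T follows a central t distribution, so

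- P(T > t*) = 0.025, which reproduces the stated error rate;
- P(T > −t*) = 1 − 0.025 = 0.975, which does not.

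This holds for any SD and any n. A simulation of 20,000 trials (800 per group, assumed log10 SD 0.6) gave 0.024 and 0.976.

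**Step 2: true ratios below the margin.** Assumed log10 SD 0.4 to 0.8, and 640 to 800 evaluable per group (640 = 800 less an assumed 20% loss). One case worked through with the normal approximation, SD 0.6, n = 800 per group, true ratio 0.60:

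- standard error = 0.6 × √(2/800) = 0.030;
- shift = (log10 0.60 − log10 0.667)/0.030 = (−0.2218 + 0.1759)/0.030 = −1.53;
- upper-bound rule: Φ(−1.53 + 1.96) = 0.67;
- lower-limit rule: Φ(−1.53 − 1.96) = 0.0002.

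Over the full assumed ranges, with the noncentral t, the chance per strain of declaring non-inferiority is:

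| True ratio | Upper-bound sentence | Lower-limit rule |
|---|---|---|
| 0.667 | 97.5% | 2.5% |
| 0.65 | 92–96% | 0.6–1.4% |
| 0.62 | 65–89% | at most 0.38% |
| 0.60 | 37–82% | at most 0.14% |
| 0.55 | 1–54% | under 0.01% |
| 0.50 | 0–20% | about 0 |

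**Step 3: where the two sentences disagree.** They differ whenever the interval contains 0.667, that is, when the observed ratio lies within 0.667 × 10^(±1.96 × SD × √(2/n)).

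- SD 0.4, n = 800: exponent 1.96 × 0.020 = 0.0392, giving 0.609 to 0.730.
- SD 0.8, n = 640: exponent 1.96 × 0.0447 = 0.0877, giving 0.545 to 0.816.

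**Step 4: the neighbouring rules.** For fever, SAP 5.1.1.2 says "The hypothesis will be supported by the data, if the upper bound of the calculated 95% CI is" below 5%. The upper bound is right there, because a higher fever rate is the worse outcome. For seroconversion, SAP 5.1.2.2.2 says "Non-inferiority for seroconversion will be demonstrated if the lower limit of the 2-sided 95% CI is" above −10%, the correct direction for an immune response. The faulty GMT sentence closely follows the fever sentence, so a carry-over is plausible, though that is an inference.

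**The case against.** The strongest reply is that the documents already settle the rule. The lower-limit statement comes first in the section, the hypotheses require it, the stated 0.025 is true only of it, and the protocol gives nothing else. Against all that stands one wrong word. The 97.5% would arise only if an analyst followed that word against everything around it, so it is not an estimate of the trial's actual error rate. The background studies in protocol 1.4 generally report similar or higher responses with the full dose, so observed ratios in the zone of disagreement were not what the sponsor expected.

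Most of this stands, and it limits the weight of the point: the planned test is not shown to be invalid. It does not remove the point. The SAP has no rule of precedence between the two statements, and the faulty one is the sentence tied to each hypothesis and to the error rate. A pre-specified criterion should be unambiguous whatever results are expected.

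A second reply is that the figures are per strain while all four strains must pass. That is correct, but if three strains are clearly above the margin, the joint GMT verdict rests on the fourth. The per-strain rates of 97.5% and 2.5% are then essentially the rates for the joint GMT claim.

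**Conclusion.** The contradiction is real and lies in the current SAP text. At the margin, the upper-bound sentence taken literally would declare non-inferiority 97.5% of the time per strain, against the 2.5% that the SAP claims and that the lower-limit rule delivers. That comparison rests on no assumption about SD or sample size. The rates below the margin and the zone of disagreement do depend on the assumed SD and evaluable numbers. The intended rule is clear from the rest of the section and the protocol, so this is a drafting error that should be corrected, and no redesign is needed. The primary fever analysis and the seroconversion rule are unaffected.

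**What to change.** In the one faulty sentence of SAP 5.1.2.2.1, replace the upper bound with the lower bound, so that it agrees with the first statement in the section, the hypotheses, the 0.025 and the protocol. Optionally, name the GMT ratio in the same sentence, since the text just before it speaks of a difference in log10 means; the 0.667 threshold already implies the ratio scale. The cost is one word in the SAP, with no change to data, sample size or protocol. It should be made before the results are seen, and the analysis program should be checked against the corrected sentence.
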